11.3. Planned interim analysis

The interim analysis is performed annually per KFDA requirements. The interim PMS report is submitted to KFDA. (Interim Analysis could be done at the time after 6-month if it's needed)

11.4. Estimated sample size

The number of subjects to be included in this PMS was determined to be 3000 subjects as per Korean regulatory authority requirements.

11.5. Analysis population

Two populations will be considered in the analysis:

- Safety population

All subjects who receive at least one dose of the drug and at least once safety assessment will be safety population. This is the primary population for the analyses of the safety data.

- Effectiveness population

All subjects who complete all procedure according to this protocol will be efficacy population. This is the primary population for the analyses for the effectiveness data.

Both analysis will be conducted based on each indications.

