5. ASSESSMENT OF PMS

5.1. Outline of PMS procedures

Table 1 Overview of PMS procedures

Visit	BASELINE	DURING TREATMENT ¹	LAST OBSERVATION ²
Check eligibility criteria	X		
Cancer information	X		
Demography	X		
Medical history	X		
Concomitant medication	X	X	X
Prescription	X	X	
Adverse events occurrence		X	X
Laboratory Test Results(optional)	X	X	X
Tumor assessments(optional)	X	X	X
Survival			X

1. The every-4week assessment of AE and tumor will be recommended. Disease assessment will be done by the study site's institutional standard.

2. Last observation is recommended to be conducted at 12 months after baseline excluding progression, death, drop-out (e.g. due to unacceptable AE/SAEs) or follow-up loss.

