8. SUBJECT COMPLETION AND WITHDRAWAL

8.1. Subject completion

All subjects who receive at least one dose of the drug and at least once safety assessment will be safety population. Last observation is recommended to be conducted at 12 months after baseline in order to evaluate safety and effectiveness. If the subject do not return to follow-up visit, all data collected until the date of last contact of the subject will be used for the analysis.

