11.6.3. Analysis of effectiveness

The percentage of subjects after administration of Votrient will be tabulated.

The percentage of subjects after administration of Votrient by age, gender, past medical history, concomitant medication, the elderly, allergy, diagnosis and indication will be calculated.

- These endpoints below by indication will be calculated **Overall Response Rate**

This is defined as the percentage of subjects achieving either a complete (CR) or partial (PR) tumor response. The response rate will be calculated from the evaluation by treating physicians of best response which records of PR and CR only. Subjects with unknown or missing response will be treated as not evaluable; i.e. they will be included in the denominator when calculating the percentage. Response rates will be compared between treatment arms using stratified Fisher's exact tests. Approximate 95% confidence limits for the difference in response rates will be calculated. Exact 95% confidence limits for the tumor response rates in each arm will also be calculated

- **Progression-free survival**

This is defined as the time from initiation of medication until the earliest date of disease progression or death due to any cause, if sooner. Date of disease progression will be based on data that is captured on the case report form. At the time of analysis, for subjects who have not progressed or died, progression-free survival will be censored at the date of discontinuation of medication.

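### The only effectiveness population is subjects who complete all procedures, an undefined criterion related to outcome, so response rate and PFS are biased in a direction that depends on how it is read

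*Protocol*

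**What the plan says.** Section 11.5 of the protocol names two populations. For safety: "All subjects who receive at least one dose of the drug and at least once safety assessment will be safety population". For effectiveness: "All subjects who complete all procedure according to this protocol will be efficacy population". Of the second it adds: "This is the primary population for the analyses for the effectiveness data". Both analyses are to be done by indication. The endpoints that depend on the effectiveness set are overall response rate (ORR) and progression-free survival (PFS) (sections 5.4, 11.2 and 11.6.3).

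Four other places bear on who is analysed.

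- **Section 5.1, Table 1.** Tumour assessments and laboratory results are marked optional, and four-weekly assessment is a recommendation. Note 2 says: "Last observation is recommended to be conducted at 12 months after baseline excluding progression, death, drop-out (e.g. due to unacceptable AE/SAEs) or follow-up loss".
- **Section 5.2.3.** Disease progression and survival are among the items recorded at the last observation.
- **Section 8.1.** On what happens when results are analysed, it says: "If the subject do not return to follow-up visit, all data collected until the date of last contact of the subject will be used". The sentence before it gives the evaluation of both safety and effectiveness as the purpose of the last observation.
- **Section 11.6.3.** For ORR: "Subjects with unknown or missing response will be treated as not evaluable; i.e. they will be included in the denominator". For PFS, events are progression or death from any cause, and subjects with neither are censored at discontinuation of medication. Section 11.2, by contrast, divides responders by those evaluable for response.

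**The concern.** Whether a subject completes is known only after treatment has begun, and it depends on tolerating the drug, staying in contact and perhaps not progressing or dying. These are the outcomes, or close relatives of the outcomes, that ORR and PFS measure. An estimate in completers does not describe the patients who started the drug. The safety set in the same section has no completion condition, so the restriction applies to effectiveness alone.

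The criterion is also not usable as written. The protocol does not say whether a subject whose last observation came early because of progression, death, drop-out or loss has completed all procedures. With optional assessments and recommended timings there is no fixed list of procedures to complete. Membership could therefore be settled after the data have been seen.

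The statistical analysis plan is not at hand and may say more. But the protocol does not leave this open: it fixes a rule, and the rule is a poor one. Section 1.1 presents the surveillance as a way to learn about effectiveness in more realistic settings, which a completer analysis does not provide.

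**Working it through.** The protocol has no figure to reproduce here. The 3000 subjects are a regulatory number, and no completion or drop-out rate is given. The calculations below only illustrate size and direction.

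**Inputs from the protocol (section 1.1).** Median PFS on pazopanib is 9.2 months in RCC and 20 weeks in STS (20 × 7 / 30.4375 = 4.6 months). The response rate is 30% in RCC; none is given for STS.

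**Assumptions.** PFS is exponential. Drop-out is independent and exponential, reaching 10% to 40% by 12 months. Completion rates by response status are invented for illustration.

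**Strict reading: a subject completes only if observed event-free at 12 months.** The event-free share with no drop-out is S(12) = 0.5^(12/median).

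- RCC: 0.5^(12/9.2) = 40.5%.
- STS: 0.5^(12/4.6) = 16.4%.

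About 60% of RCC and 84% of STS subjects would be removed by the PFS event itself. Multiplying by 0.9 to 0.6 for drop-out leaves 36% to 24% of RCC and 15% to 10% of STS subjects. Twelve-month PFS among those kept is 100% by construction.

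**Lenient reading: progression or death counts as completion; drop-outs and losses are removed.** Let λ = ln 2 / median, μ = −ln(1 − d)/12 for drop-out d by 12 months, and B = exp(−12(λ + μ)), the share event-free and still observed at 12 months. The share kept is K = B + [λ/(λ + μ)](1 − B), and 12-month PFS among those kept is B/K.

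For RCC at d = 10%: λ = 0.0753, μ = 0.0088, B = 0.364, K = 0.364 + 0.896 × 0.636 = 0.934, and B/K = 0.390. The median t solves [λ/(λ + μ)](1 − exp(−(λ + μ)t)) = K/2, which gives 8.76 months.

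| | All treated, censored | Lenient, d = 10% | Lenient, d = 40% |
|---|---|---|---|
| RCC: kept | 100% | 93.4% | 72.7% |
| RCC: median PFS (months) | 9.2 | 8.76 | 7.13 |
| RCC: 12-month PFS | 40.5% | 39.0% | 33.4% |
| STS: kept | 100% | 95.3% | 80.1% |
| STS: median PFS (months) | 4.6 | 4.40 | 3.73 |
| STS: 12-month PFS | 16.4% | 15.5% | 12.3% |

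PFS falls because those removed were event-free when they left. Censoring would have kept their event-free time; deletion loses it.

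**ORR.** With true rate p = 0.30 and completion rates c1 in responders and c0 in non-responders, the rate in completers is p·c1 / [p·c1 + (1 − p)·c0].

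- 80% / 70%: 0.24 / (0.24 + 0.49) = 32.9%.
- 90% / 70%: 0.27 / (0.27 + 0.49) = 35.5%.
- 80% / 50%: 0.24 / (0.24 + 0.35) = 40.7%.
- 90% / 50%: 0.27 / (0.27 + 0.35) = 43.5%.
- Pattern reversed, 70% / 90%: 0.21 / (0.21 + 0.63) = 25.0%.

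The rate stays at 30% only when c1 = c0.

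**The case against.** The strongest reply is that the strict reading fits the protocol badly. Note 2 to Table 1 only recommends 12 months and excepts progression, death, drop-out and loss. Section 5.2.3 collects progression and survival at the last observation, and section 11.6.3 makes progression and death the PFS events. A subject who progresses at month 4 can have a last observation and be complete; otherwise the PFS endpoint would have almost nothing to count. This stands, so the 60% and 84% exclusions are what one reading would produce, not what the plan predicts. Nor is the lenient reading secured: note 2 lists drop-out and loss alongside progression and death, so separating them is an interpretation too.

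A reader might infer that both endpoints are biased upward. The documents do not support that: on the lenient reading PFS goes down, and the direction for ORR depends on completion rates that the protocol does not give.

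A reader might also see flat contradictions with sections 8.1 and 11.6.3. That goes too far. Section 8.1 does not name the population of the analysis it refers to, so the safety analysis could satisfy it. Because tumour assessment is optional, a subject could complete everything required without a response on record, stay in the set and be counted under 11.6.3. The PFS censoring rule would likewise still apply to event-free completers. What remains is tension: data to last contact, missing responses in the denominator and censoring all sit more naturally with a set that includes people who stop early.

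Finally, effectiveness is secondary in a single-group surveillance without a control, and neither the safety set nor the sample size depends on it. That is correct and limits the severity. It does not repair the definition.

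**Conclusion.** The point holds. The primary and only effectiveness population is conditioned on an undefined post-baseline criterion that is related to outcome, and nothing elsewhere in the protocol corrects it.

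The direction of the bias in PFS turns on the undefined term. It is upward if progression or death means non-completion, with 12-month PFS at 100% in the extreme. It is downward if only drop-outs and losses are deleted: an RCC median of about 7.1 to 8.8 months against 9.2, and an STS median of about 3.7 to 4.4 against 4.6. ORR is distorted whenever completion differs by response: from 30% to about 33-44% under the assumed rates, or to 25% with the pattern reversed. These figures rest on exponential PFS, independent drop-out of 10-40% and assumed completion rates. The 30% applies to RCC only. A general claim of inflation, or of a known share excluded, is not supported.

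This should be fixed. It affects both effectiveness endpoints in both indications, but not the primary safety analysis.

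**What to change.** 1. Define the primary effectiveness population as all subjects in each indication who received at least one dose, and say so consistently in sections 8.1, 11.5 and 11.6.3.
2. Analyse PFS in all of them, with incomplete follow-up censored, not excluded.
3. Report ORR by indication on the same set. Reconcile the denominator in 11.2 (evaluable subjects only) with that in 11.6.3 (non-evaluable subjects included), and show ORR among subjects with a post-baseline tumour assessment as a supportive figure.
4. Keep completers only as a labelled sensitivity set, with a written definition of completion that says how progression, death, drop-out and loss are classified.

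The cost is wording in the protocol and any analysis plan; no new data are needed. The downside is that, with tumour assessment optional, counting unassessed subjects as non-responders makes the all-treated ORR conservative, which is why the supportive figure should stand beside it.

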11.6. Final analyses

11.6.1. Analysis of demographics/baseline characteristics

Demographic characteristics (age, gender, etc.) will be tabulated.

11.6.2. Analysis of safety

The percentage of subjects reporting each individual adverse event after administration of Votrient will be tabulated with 95% confidence interval. Cases with serious adverse events and/or unexpected adverse events will be described in detail. The distribution of adverse events by frequency, severity, outcome, investigator's causal assessment will be tabulated.

The percentage of subjects reporting adverse event by age, gender, past medical history, concomitant medication, the elderly, allergy, and diagnosis will be calculated.

CONFIDENTIAL

Votrient PMS

Protocol Ver.2

Study identifier:115578

GlaxoSmithKline Korea

The percentage of subjects reporting adverse events among special care population such as the elderly, hepatic impairment subjects, renal impairment subjects or cardiovascular disease subjects will be tabulated respectively.

11.6.3. Analysis of effectiveness

The percentage of subjects after administration of Votrient will be tabulated.

The percentage of subjects after administration of Votrient by age, gender, past medical history, concomitant medication, the elderly, allergy, diagnosis and indication will be calculated.

- These endpoints below by indication will be calculated **Overall Response Rate**

This is defined as the percentage of subjects achieving either a complete (CR) or partial (PR) tumor response. The response rate will be calculated from the evaluation by treating physicians of best response which records of PR and CR only. Subjects with unknown or missing response will be treated as not evaluable; i.e. they will be included in the denominator when calculating the percentage. Response rates will be compared between treatment arms using stratified Fisher's exact tests. Approximate 95% confidence limits for the difference in response rates will be calculated. Exact 95% confidence limits for the tumor response rates in each arm will also be calculated

- **Progression-free survival**

This is defined as the time from initiation of medication until the earliest date of disease progression or death due to any cause, if sooner. Date of disease progression will be based on data that is captured on the case report form. At the time of analysis, for subjects who have not progressed or died, progression-free survival will be censored at the date of discontinuation of medication.

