Pazopanib (Votrient) is a potent multi-target receptor tyrosine kinase inhibitor of vascular endothelial growth factor receptors (VEGFR) -1, -2 and -3, platelet-derived growth factor receptors (PDGFR) $-\alpha$ and $-\beta$, and stem cell factor receptor (c-kit). [kumar, 2007] VEGFR regulates angiogenesis [Kerbel, 2008] and PDGFR regulates angiogenesis and proliferation of some tumour cells [Yu et al, 2003, Homsy et al, 2007]. And c-Kit regulates cellular proliferation, survival and metastasis. [Demetri, 2001] Pazopanib targets these key molecules involved in tumour angiogenesis. [Sonpavde et al, 2008] Pazopanib is a more selective multikinase inhibitor compared with sunitinib. [Kumar et al, 2009] Besides VEGFR, PDGFR and c-Kit, sunitinib inhibits 49 additional kinases. By contrast, pazopanib inhibit seven additional kinases. And pazopanib has a greater affinity to VEGFR-2 than sunitinib. [Kumar et al, 2009, Karamen et al, 2008]

Clinical efficacy and safety of pazopanib in treating advanced RCC patients have been established in a randomized double-blind placebo-controlled Phase III study that enrolled 435 treatment-naïve or cytokine-pretreated subjects. PFS was significantly prolonged with pazopanib compared with placebo in the overall study population (median, PFS 9.2 v 4.2 months; hazard ratio [HR], 0.46; 95% CI, 0.34 to 0.62; $P < 0.0001$), the treatment-naïve subpopulation (median PFS 11.1 v 2.8 months; HR, 0.40; 95% CI, 0.27 to 0.60; $P < 0.0001$), and the cytokine-pretreated subpopulation (median PFS, 7.4 v 4.2 months; HR, 0.54; 95% CI, 0.35 to 0.84; $P < 0.001$). The objective response rate was 30% with pazopanib. [Sternberg et al, 2010]

Soft Tissue Sarcoma (STS) is a rare group of heterogeneous mesenchymal cancers originating from connective tissue. The annual incidence of STS is around 2-3/100,000. Overall, STS account for approximately 1% of all malignancies, while they give rise to 2% of the total cancer-related mortality. The 5-year survival in Europe for adult STS (excluding visceral STS) averages 60%, with substantial geographic variations. [Storm et al, 1998] The median survival time in patients with metastatic STS is usually < 12 months.

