5.4. Effectiveness Assessment

Effectiveness of Votrient is secondary end point of Votient PMS

- Overall response rate by RECIST 1.1 : (CR+PR)/evaluable for response
 - As a appendix 2, tumour evaluation can be done using RECIST 1.1 criteria
- Progression free survival (PFS)

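### The overall response rate has two incompatible denominators: evaluable subjects only in sections 5.4 and 11.2, not-evaluable subjects included in section 11.6.3

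*Protocol*

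**What the plan says.** Section 5.4 gives the effectiveness endpoint as "Overall response rate by RECIST 1.1 : (CR+PR)/evaluable for response", and section 11.2 repeats that definition among the secondary endpoints. Neither section defines who is evaluable.

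Section 11.6.3 describes the analysis. It defines the rate without restricting it to evaluable subjects: "This is defined as the percentage of subjects achieving either a complete (CR) or partial (PR) tumor response". It then gives the only rule for missing response in the protocol: "Subjects with unknown or missing response will be treated as not evaluable; i.e. they will be included in the denominator when calculating the percentage".

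Three other statements bear on the point:

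- Section 11.5 limits the population in which effectiveness is analysed: "All subjects who complete all procedure according to this protocol will be efficacy population". It adds that the analyses are done separately for each indication.
- Table 1 in section 5.1 marks tumour assessment as optional at baseline, during treatment and at the last observation. Its first footnote recommends assessment every 4 weeks and leaves disease assessment to each site's standard.
- Section 11.4 sets the total at 3000 subjects by regulatory requirement, with no split between renal cell carcinoma and soft tissue sarcoma.

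**The concern.** Two rules are fixed for one endpoint, and they treat the same subjects in opposite ways. This is more than detail left for a statistical analysis plan to fill in: a plan that adopts either rule departs from the protocol in at least one place.

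The two rates also differ in a known direction. The evaluable-only rate can never be below the inclusive one, and it is higher whenever any response is missing and there is at least one responder. Section 11.3 foresees annual interim reports to the regulator and section 12.6 foresees public disclosure of effectiveness results. While both rules stand, either rate could be presented as the protocol's own, and reports could differ in which one they use.

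The optional status of tumour assessment is what makes this matter in practice, because the design itself allows subjects to have no response on record.

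**Working it through.** **Reading the sections together.** The protocol states no expected response rate, power or precision for this endpoint, so there is no figure of its own to reproduce. The check is first one of wording.

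| Section | Denominator | Subject with unknown or missing response |
|---|---|---|
| 5.4 | evaluable for response | excluded |
| 11.2 | evaluable for response | excluded |
| 11.6.3 | includes those called not evaluable | included |

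The sections could be reconciled only if evaluable meant everyone in the effectiveness population. Subjects labelled not evaluable would then have to count as evaluable, which the wording of 11.6.3 rules out. Section 11.5 decides who enters the analysis. It does not choose between the two denominators within that group.

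**Inputs for scale.**

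- Response rate among evaluable subjects: 30%, from section 1.1 ("The objective response rate was 30% with pazopanib"). This is the renal cell carcinoma trial and serves only as illustration. The protocol gives no response rate for soft tissue sarcoma.
- Share with unknown or missing response, m: not given in the protocol. Assumed 10% to 40%.
- Number analysed per indication: not given. Assumed 1000 for the interval comparison, with 500 and 300 as smaller cases.

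**Relation between the two rates.** With N subjects in the analysis, (1 − m)N have a known response. A subject without one cannot be in the numerator, so the number of responders, x, is the same under both rules:

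- evaluable-only rate = x / [(1 − m)N]
- inclusive rate = x / N = (1 − m) × evaluable-only rate

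| m | Evaluable-only | Inclusive | Gap (points) |
|---|---|---|---|
| 0% | 30% | 30% | 0 |
| 10% | 30% | 0.90 × 30% = 27% | 3 |
| 20% | 30% | 0.80 × 30% = 24% | 6 |
| 30% | 30% | 0.70 × 30% = 21% | 9 |
| 40% | 30% | 0.60 × 30% = 18% | 12 |

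**Against sampling error.** The approximate 95% half-width at 30% is 1.96 × √(0.30 × 0.70 / n): 2.8 points at n = 1000, 4.0 at n = 500 and 5.2 at n = 300. A 3-point gap is therefore about one half-width at 1000 and less than one at 500.

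Exact (Clopper-Pearson) 95% intervals with N = 1000:

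- m = 10%: 270/900 = 30.0% (27.0 to 33.1) against 270/1000 = 27.0% (24.3 to 29.9). The intervals overlap.
- m = 20%: 240/800 = 30.0% (26.84 to 33.31) against 240/1000 = 24.0% (21.38 to 26.77). They just fail to overlap.
- m = 30%: 210/700 = 30.0% (26.6 to 33.6) against 210/1000 = 21.0% (18.5 to 23.7). They are clearly apart.

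The intervals are only a yardstick. Both rates come from the same responders, so the gap between them is fixed by m and does not shrink as N grows.

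**The case against.** The strongest objection concerns how much depends on this. Response rate is one of several secondary endpoints in a single-group, non-interventional surveillance whose primary endpoint is the occurrence of adverse events. The 3000 subjects are a regulatory number. No safety conclusion and no sample-size figure changes. All of that stands.

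The size is also uncertain. Table 1 makes tumour assessment optional, but its footnote recommends it every 4 weeks, and 11.5 admits only subjects who completed all procedures. If completion is read to require a tumour assessment, few missing responses remain and the gap could be close to zero. That stands for the numbers. It does not settle the definitions, which would still conflict.

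A reader might infer three stronger things that the documents do not support:

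- That with 3000 subjects the gap far exceeds sampling error. Effectiveness is analysed by indication and in completers, so 3000 is not the denominator of any planned response rate. At 10% missing the gap is within ordinary sampling error for 500 subjects.
- That the group without a response will be large. The protocol gives no share. Optional assessment makes a sizeable group plausible, not certain.
- That the rule will be chosen after the data are seen. A statistical analysis plan may exist that fixes it. The protocol shows only that it does not settle the choice itself.

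Finally, one can object that scoring never-imaged patients as non-responders makes the rate partly a measure of imaging practice, so a preference for that denominator is a judgement. This is fair, and it is the reason for showing both rates.

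**Conclusion.** The contradiction is real and lies in operative text: one named endpoint has two definitions that cannot both be applied, and no rule of precedence. It needs correcting, as a fault in a secondary endpoint only.

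The inclusive rate is (1 − m) times the evaluable-only rate. On an illustrative 30% and an assumed m of 10% to 40%, the gap is 3 to 12 percentage points. This rests on the renal cell carcinoma figure, on a missing share that the protocol does not state, and on taking evaluable to mean having a known response. Whether the gap exceeds sampling error depends on m and on the number per indication, neither of which is given. The gap narrows if completion under 11.5 is taken to require tumour assessment.

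**What to change.** Use one headline denominator in 5.4, 11.2 and 11.6.3, and align the effectiveness population in 11.5 with it. Changing the first three alone would leave a new conflict, because 11.5 now admits completers only.

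The preferable choice follows the one explicit missing-data rule already in the protocol, that of 11.6.3:

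- **Headline rate (5.4, 11.2, 11.6.3):** CR plus PR divided by all treated subjects in the indication. In 11.6.3, replace the term not evaluable by non-responders for subjects with unknown or missing response.
- **Population (11.5):** make all treated subjects in the indication the population for this rate.
- **Supportive rate:** define evaluable for response as having a baseline and at least one post-baseline tumour assessment. Report CR plus PR over that group beside the headline rate, with the number excluded, for each indication.

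The cost is wording in four places and no new data collection. The headline rate will be lower, and with optional imaging it will partly reflect how often sites assess tumours. The supportive rate and its count of excluded subjects make that visible. If the sponsor prefers the evaluable-only rate as the headline, the contradiction can be removed that way too, provided the term is defined, all four sections agree and the number left out is reported.

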8.2. Subject withdrawal

Subjects who are withdrawn because of SAEs/AEs must be clearly distinguished from subjects who are withdrawn for other reasons. Investigators will follow subjects who are withdrawn as result of a SAE/AE until resolution of the event. Withdrawals will not be replaced.

A subject is considered a 'withdrawal' from the PMS when no PMS procedure has occurred, no follow-up has been performed and no further information has been collected for this subject from the date of withdrawal/last contact.

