9.4. Recording of AEs and SAEs

When an AE/SAE occurs, it is the responsibility of the investigator to review all documentation (e.g., hospital progress notes, laboratory, and diagnostics reports) relative to the event. The investigator will then record all relevant information regarding an AE/SAE on the CRF.

It is not acceptable for the investigator to send photocopies of the subject's medical records to GSK in lieu of completion of the appropriate AE/SAE CRF pages. However, there may be instances when copies of medical records for certain cases are requested by GSK. In this instance, all subject identifiers will be blinded on the copies of the medical records prior to submission to GSK.

The investigator will attempt to establish a diagnosis of the event based on signs, symptoms, and/or other clinical information. In such cases, the diagnosis should be documented as the AE/SAE and not the individual signs/symptoms.

From the time a subject agree to his or her participating in this PMS until one month after he or she has completed Votrient treatment (including any follow-up period), AE/SAE will be reported promptly to GSK.

Any signs and symptoms present at the time the first dose is administered will be documented as baseline signs and symptoms. Any medical occurrences which present after administration of the medication and on or before the final follow up visit must be reported as Adverse Events. All AEs must be recorded irrespective of whether they are considered drug related. At each visit/assessment in the period defined above, AEs/SAEs will be evaluated by the investigator and recorded. Any AEs/SAEs already documented at a previous assessment and designated as ongoing, should be reviewed at subsequent visits as necessary. If these have resolved, this should be documented. If an AE changes in intensity then the maximum intensity should be captured in the CRF.

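### The PFS censoring rule gives no date for event-free subjects still on drug, and it counts events after stopping while discarding event-free time after stopping

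*Protocol*

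**What the plan says.** Section 11.6.3 of the protocol defines PFS as "time from initiation of medication until the earliest date of disease progression or death due to any cause, if sooner". Nothing limits events to time on drug. The same paragraph then fixes one censoring date for everyone without an event: "for subjects who have not progressed or died, progression-free survival will be censored at the date of discontinuation of medication".

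Observation is not tied to time on drug:

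- The footnote to Table 1 (section 5.1) says: "Last observation is recommended to be conducted at 12 months after baseline excluding progression, death, drop-out (e.g. due to unacceptable AE/SAEs) or follow-up loss". The clock starts at baseline, but drop-out may end observation earlier.
- Section 5.2.3 lists disease progression and survival among the items of the last observation.
- Section 9.4 runs adverse event reporting to one month after the end of treatment.
- Section 8.2 states: "Investigators will follow subjects who are withdrawn as result of a SAE/AE until resolution of the event".
- Section 8.1, for subjects who do not return, says that "all data collected until the date of last contact of the subject will be used for the analysis".

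Table 1 marks tumour assessments as optional and its footnote recommends them every 4 weeks. Section 11.3 plans annual interim analyses.

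**The concern.** The rule uses a treatment date to end follow-up for an endpoint that is not a treatment endpoint.

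1. **No date.** A subject still taking the drug without progression has no discontinuation date, so the rule cannot be applied. These are subjects with good outcomes, and the analyst has to invent a date that the protocol does not give.
2. **Censoring that depends on the later outcome.** A subject who stops at month 3 and progresses at month 9 is an event at month 9. A subject who stops at month 3 and is documented progression-free at month 12 is censored at month 3. Kaplan-Meier estimation requires that being censored does not depend on what happens afterwards. Here it does, and the risk set is too small.
3. **Credited time.** Because scans are optional, the last one may precede the stop date. The gap is then counted as progression-free although nobody looked.

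The second fault lowers the PFS curve and the third raises it.

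**Working it through.** The protocol gives no PFS target, event count or precision for this surveillance, so there is no figure of its own to reproduce. The check asks what the written rule does to a known curve.

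**Inputs from the protocol (section 1.1).** Median PFS on pazopanib: RCC 9.2 months; STS 20 weeks = 20 × 7 / 30.44 = 4.6 months. Planned observation: 12 months (section 5.1).

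**Assumptions, not in the protocol.** Exponential PFS, S(t) = 2^(−t/median). A share p = 10-40% would stop for reasons other than progression by month 12, independently of PFS, so the chance of still being on drug is G(t) = (1 − p)^(t/12). After stopping, each subject is observed for c = 0, 1, 3 or 12 months, never beyond month 12.

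**Step 1: subjects without a date.** Event-free at 12 months: RCC 2^(−12/9.2) = 40.5%; STS 2^(−12/4.6) = 16.4%. Event-free and still on drug is S(12) × (1 − p):

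| p | RCC | STS |
|---|---|---|
| 10% | 0.405 × 0.9 = 36.4% | 0.164 × 0.9 = 14.8% |
| 20% | 32.4% | 13.1% |
| 30% | 28.3% | 11.5% |
| 40% | 0.405 × 0.6 = 24.3% | 0.164 × 0.6 = 9.8% |

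As a share of all subjects recorded as event-free, this is 90% down to 47% (RCC) and 90% down to 33% (STS) over the values of p and c.

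**Step 2: the asymmetry.** To isolate it, on-drug subjects are given a month-12 date that the rule itself does not supply. With f the density of PFS, events are recorded at time t with density e(t) = f(t)·G(t − c), taking G = 1 before time 0. An event-free stopper leaves the risk set at the stop date. If R(t) is the share still at risk, the Kaplan-Meier curve tends to exp(−∫ e/R).

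- c = 0: R(t) = S(t)·G(t) and e/R = f/S, so there is no bias.
- c = 12: R(t) = S(t) − S(12)·[1 − G(t)], which is smaller than the correct S(t). RCC at month 6: S(6) = 0.636. With p = 40%, G(6) = 0.775 and R(6) = 0.636 − 0.405 × 0.225 = 0.545, so the hazard is overstated by 0.636/0.545 = 1.17. With p = 10%, R(6) = 0.636 − 0.405 × 0.051 = 0.615, a factor of 1.03.

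Integrating numerically for RCC (correct values: median 9.2 months, 12-month PFS 40.5%):

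| Off-drug observation | Median, p = 10 / 20 / 30 / 40% | 12-month PFS, % |
|---|---|---|
| none | 9.2 / 9.2 / 9.2 / 9.2 | 40.5 throughout |
| 1 month | 9.1 / 9.0 / 9.0 / 8.9 | 40.2 / 39.9 / 39.5 / 39.0 |
| 3 months | 9.0 / 8.8 / 8.6 / 8.4 | 39.7 / 38.9 / 37.9 / 36.8 |
| to month 12 | 9.0 / 8.7 / 8.5 / 8.3 | 39.0 / 37.4 / 35.5 / 33.2 |

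Simulation with 400,000 subjects per scenario agrees (to month 12: median 8.95 down to about 8.25). For STS the median stays between 4.6 and 4.3 months, and 12-month PFS falls from about 16% to between 16% and 12% with observation to month 12.

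**Step 3: credited time.** The size depends on the gap between last assessment and drug stop. The protocol does not allow an estimate of that gap, so only the direction (upward) can be given.

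**The case against.** **Importance.** PFS is a secondary endpoint in a single-group surveillance with no control and no stated PFS hypothesis. The sample size is set by regulation and the primary endpoint is adverse events. This stands: a reader might infer that the fault undermines the study, and it does not.

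**Size.** A reader might take the largest figures (RCC median down to 8.3 months, 12-month PFS 33%) as the expected bias. They need every subject who stops to be observed for progression to month 12. Section 5.1 names drop-out for unacceptable adverse events among the exceptions to the 12-month observation, section 9.4 guarantees only one month of event reporting after treatment, and section 8.2 follows withdrawals for resolution of the event, not for progression. The bias therefore runs from zero upward. The stopping rates and their independence from PFS are also assumptions. If stopping is related to prognosis, censoring is informative in a direction the protocol does not fix.

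**Population.** Section 11.5 limits the effectiveness population to subjects who complete all procedures, so some early drop-outs may not enter the analysis. The calculation includes everyone and is an illustration, not a forecast.

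**Subjects still on drug.** It is tempting to call them the largest censored group. They are in many scenarios, but at 40% stopping their share of the event-free can be as low as 47% (RCC) or 33% (STS). It is also tempting to assume they would be dropped, which would cut the RCC median to about 4.9-5.9 months. The protocol does not say so. Section 8.1 shows an intention to use data to last contact, but it covers subjects who do not return and sets no PFS date.

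None of this supplies the missing date. Nor is it a detail left for a later analysis plan: the protocol states a rule for all event-free subjects, and it cannot be carried out for some of them.

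**Conclusion.** The point holds as a fault that should be fixed in a secondary, descriptive endpoint.

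- **Missing date:** this follows from the text alone. Only its extent (about 36-24% of RCC and 15-10% of STS subjects at month 12) rests on exponential PFS and on 10-40% stopping for other reasons.
- **Asymmetry:** real and downward when stopping is independent of PFS. It is nil without off-drug observation, 0.1-0.3 months on the RCC median with one month, and at most about 0.9 months and 7 percentage points of 12-month PFS with full observation to month 12.
- **Credited time:** upward, unquantified. The net direction in the final report therefore cannot be stated in advance.

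**What to change.** Replace the censoring sentence in section 11.6.3 with:

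> *Subjects without progression or death will be censored at the last date on or before the data cut at which they were documented alive and progression-free (last tumour or disease assessment, or last observation if no scan was done), whether or not Votrient has been discontinued.*

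Align it with section 8.1, so that data to last contact are used in the same way in both places.

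The fallback to last observation matters. The common convention of censoring unscanned subjects on day 1 would partly recreate the asymmetry, because scans are optional while progression and survival are also recorded at last observation. If a share u of RCC subjects has no scan but their events are still captured, the curve becomes (S(t) − a)/(1 − a) with a = u × 0.405. For u = 10%, 12-month PFS is (0.405 − 0.0405)/(1 − 0.0405) = 38%, and the median is reached where S(t) = 0.5 + a/2 = 0.520, at 8.7 months. For u = 20% the values are 35% and 8.2 months.

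The current rule may stay as a sensitivity analysis if off-drug events are then not counted and subjects still on drug are given the data-cut date.

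Cost: one sentence in the protocol. Subjects with few or no post-baseline assessments will contribute little follow-up. Assessment dates must be on the case report form. The protocol lists tumour evaluation at each stage but does not show that its date is recorded, so this needs checking.
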